9.4.5 Censored Cases

Data for patients where a protocol deviation occurred which could affect patient outcome will be censored from the Efficacy and Safety Patient Populations. They will be reported on separately.

If a case receives a unicompartmental knee arthroplasty in the contralateral compartment of the study knee, this case will be considered a deviation and censored from analysis for all areas except survivorship. This case will be included in the survivorship analysis only.

10 Study Procedures

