2.2 Safety

Reported protocol defined adverse events will be compared to literature. It is expected that the adverse event rates reported for the Triathlon® PKR Unicompartmental Knee System will be comparable to those reported in the literature.

3 Clinical Study Plan

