8.1 Adverse Event (AE) Reporting Requirements for this study

- All adverse events that meet the definition of serious (not to include elective surgeries)
- All AE's related to operative site, regardless of seriousness

See Adverse Event Decision Tree - Figure 1

Adverse Event Reporting Period

The study period during which adverse events must be reported is normally defined as the period from the initiation of any study procedures to the end of the study treatment follow-up. In other words, the start of study procedures is considered to be the point of consent. Therefore, any adverse events which fit the protocol defined reportable events must be reported from the time of obtaining consent throughout the study duration.

At each contact with the subject, the investigator must seek information on adverse events by specific questioning and, as appropriate, by examination. Information on protocol defined adverse events should be recorded immediately in the source document, and also in the appropriate adverse event module of the case report form (CRF). All clearly related signs, symptoms, and abnormal diagnostic procedure results should be recorded in the source document, though they should be grouped under one diagnosis. The clinical course of each event should be followed until resolution or until it is determined at the end of the study that the adverse event will not resolve.

During the medical record review of the retrospectively enrolled cases, any operative site adverse events will be documented as per the usual procedure. For prospective follow-up, these cases will adhere to the adverse event reporting described above.

General Physical Examination Findings

At screening for inclusion into the study, any clinically significant abnormality should be recorded as a preexisting condition. During the study, any new clinically significant findings/abnormalities that meet the definition of a protocol defined adverse event must also be recorded and documented as an adverse event.

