9.4.3 Efficacy Patient Populations

Per Protocol Population:

All subjects other than those censored who received the Triathlon® PKR Unicondylar Knee System. Data for patients where a protocol deviation occurred which could affect patient outcome will not be included.

The primary and secondary efficacy analyses will be based on the per protocol population.

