9.4.4 Safety Patient Population

Safety Population

The safety population will include all non-censored subjects who received the Triathlon® PKR Unicondylar Knee System.

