12.3 Expected Complications and Rates of Occurrences

The safety objective will compare the Triathlon® PKR rates to the literature rates at 10 years. Percentages for UKA have been taken from published literature and represent averages or ranges as noted.

Table I
Unicompartmental Knee Arthroplasty Adverse Event Literature Summary

Event	Unicompartmental Knee Replacement PUBLISHED LITERATURE		
	N=	Rate	Mean follow-up
Related to Surgery			
Femoral fracture intra-op	72 kns	1 event - 1%8	40.2 months
Tibial fracture /intra-op	72 kns	3 events - 4% ⁸	40.2 months
Patellar fracture	Not available		

Event	Unicompartmental Knee Replacement PUBLISHED LITERATURE		
	N=	Rate	Mean follow-up
/intra-op			
Supracondylar fracture/intra-op		Not available	
Superficial wound infection	88 cases/79 pts 212 kns	2 event - 2% ⁹ 1 event - 1% ¹⁰	9 years unknown
Deep joint infection	79 kns/69 pts 56 kns/56 pts 212 kns 514 kns 203 kns/174 pts 2288 kns 318 kns/270 pts	2 events - 2.7% ¹¹ 1 event - 2% ¹ 2 events - 1 % ¹⁰ 1 event - 1 % ¹⁰ 2 events - 1% ¹² 5 events - <1% ¹³ 1 event - <1% ¹⁴	3.35 years (40.2 mnths) 2 years unknown 2-year follow-up 14.8 years 10-year follow-up 8 months
Wound related (non-infected)	88 cases/79 pts 212 kns	1 instance - 1% ⁹ 1 event - 1 % ¹⁰	9 years unknown
Peroneal nerve palsy		Not available	
Other operative	62 kns/51 pts 62 kns/51 pts 41 kns/41 pts 26 kns/17 pts 26 kns/17 pts 30 kns/28 pts 30 kns/28 pts 56 kns/56 pts 56 kns/56 pts 212 kns 212 kns 212 kns	2 MCL avulsions - 3% ¹⁵ 1 MCL avulsion - 2% ^{Error! Bookmark not} defined. 1 MCL fracture - 2% ¹⁶ 1 hemarthrosis - 4% ¹⁷ 1 arthrolysis - 3% ¹⁸ 1 mobilization - 3% ¹⁸ 2 events to remove loose bodies - 4% ¹ Clicking sensation - 2% ¹ 9 cement fragments - 4% ¹⁰ 3 partial lat menisectomies-1% ¹⁰ 1 femoral trochlea chondroplasty-1% ¹⁰ 1 osteochondral loose body removal - 1% ¹⁰	7.5 years 12 years 2 years 6.9 years 6.9 years 7-10-year follow-up 7-10-year follow-up 2 years 2 years unknown unknown
Related to Implant			
Prosthesis fracture/femoral component	88 cases/79 pts 203 kns/174 pts	4 events - 5% ⁹ 2 events - 1% ¹²	9 years 14.8 years
Prosthesis fracture/tibial component	30 kns/28 pts	1 event - 3% ¹⁸	7-10 year follow-up
Prosthesis fracture/tibial insert	30 kns/28 pts 75 kns/62 pts	1 event - 3% ¹⁸ 17 events - 23% ¹⁹	7-10-year follow-up 18 months
Prosthesis fracture/patellar component		Not available	

Event	Unicompartmental Knee Replacement PUBLISHED LITERATURE		
	N=	Rate	Mean follow-up

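### The safety population leaves out implanted knees with an outcome-relevant deviation or a contralateral-compartment UKA, so the adverse event rates compared with literature omit their events

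*Combined protocol and SAP*

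**What the plan says.** **Who is in the safety population.** Section 9.4.4: "The safety population will include all non-censored subjects who received the" study device. Section 9.4.5 defines the censoring: "Data for patients where a protocol deviation occurred which could affect patient outcome will be censored from the Efficacy and Safety Patient Populations". It adds: "They will be reported on separately". For a knee given a UKA in its contralateral compartment, section 9.4.5 says "this case will be considered a deviation and censored from analysis for all areas except survivorship", and its next sentence confines the case to survivorship.

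**What is collected and summarised.** Section 8.1 makes reportable "All AE's related to operative site, regardless of seriousness", as well as all serious events other than elective surgery. Section 9.2.1 takes every reported protocol-defined event as a safety parameter. Section 9.2.2 promises that all events will be tabulated with rates and exact 95% confidence intervals. It names no analysis set.

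**What the rates are for.** Section 2.2: "Reported protocol defined adverse events will be compared to literature". Section 12.3 sets the comparison as "PKR rates to the literature rates at 10 years".

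**Survivorship.** Section 9.1.2 defines the endpoint as revision or removal of any component. Section 9.4.3 says "The primary and secondary efficacy analyses will be based on the per protocol population", a set that excludes censored cases, while section 9.4.5 keeps the contralateral-UKA knee in survivorship.

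**The concern.** A rule that removes patients because a deviation could influence their outcome is ordinary for a per protocol efficacy set. Applied to the safety set, it takes knees that carry the device out of the numerator and the denominator of the rates the study exists to compare. Those rates then describe deviation-free use, while the section headed Safety Analysis promises all events.

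The dropped knees may also differ in risk. Section 11.5 lists eligibility breaches among major deviations, BMI above 35 is an exclusion (section 4.2), and the labelling in Appendix C links obesity to failure of fixation. The plan does not say that such a breach triggers the 9.4.5 rule. If it did, the compared rates could be too low.

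For the contralateral UKA, section 9.4.5 gives no timing. Use at the index surgery has a basis as a deviation, because the labelling warns against repairing both condyles of one knee simultaneously. A UKA added later is a further operation on the study knee, which is a postoperative event, yet the rule keeps it out of the adverse event tables.

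**Working it through.** **Plan's own figures.** The plan gives no number of deviations or contralateral UKAs, so there is none to reproduce on this point. The denominator can be confirmed: (21 × (1.645 + 0.842) / 6)² = 75.7, so 76; 76 / 0.80 = 95; 95 + 80 prospective knees = 175 (sections 3.3 and 9.4.1).

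**Reading the sections together.** Section 9.2.2 names no population, and section 9.4.4 defines the only safety set, so I take the 9.2.2 rates to be computed on it. An operative-site event in a censored knee is then reported under 8.1 and is a safety parameter under 9.2.1, but is not in the main rate. For deviation cases it appears in a separate report of unspecified content. For contralateral-UKA cases the survivorship-only sentence leaves even that uncertain.

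**Deviation knees.** Inputs:
- N = 175 knees (section 3.3).
- d = 9 or 18 knees dropped, about 5% or 10% (assumed).
- r = 7% event rate in the kept knees. This borrows one Table I entry, 36 of 516 femoral-component revisions at 10 years.
- RR = risk in dropped knees relative to kept knees (assumed).

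The main table shows r. The all-implanted rate is [(N − d) × r + d × r × RR] / N, so the gap is r × (RR − 1) × d / N.

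| d | RR = 1 | RR = 2 | RR = 3 |
|---|---|---|---|
| 9 | 7.00% | 7.36% | 7.72% |
| 18 | 7.00% | 7.72% | 8.44% |

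The largest gap is 0.07 × 2 × 18 / 175 = 1.4 points. At RR = 0.5 with d = 18 the sign reverses: 0.07 × (−0.5) × 18 / 175 = −0.4 points, so the main table would overstate. The gap grows with r and RR. With an assumed 10% base rate, 18 knees dropped and four times the risk, whole-knee counts are 16/157 = 10.2% in the safety population against 23/175 = 13.1% in all implanted knees.

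**Precision for scale.** 12/175 = 6.9%, exact 95% interval 3.6% to 11.7%.

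**Contralateral UKA.** A later UKA counted as a reoperation contributes nothing to the main table under 9.4.5, whatever the true number. In an all-implanted table each case adds 1/175 = 0.57 points, or 1/80 = 1.25 points within the prospective cohort.

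**Survivorship (minor).** With 80 prospective knees and no loss to follow-up, counting one such case as an event lowers crude survival by 1.25 points. With 8 revisions and 2 added UKAs, survival is 72/80 = 90.0% if they are non-events and 70/80 = 87.5% if they are events.

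**The case against.** The strongest defence is that nothing is hidden. Section 9.4.5 promises separate reporting, section 9.2.2 promises a listing of all events, and the literature comparison has no hypothesis, margin or threshold. Every count above is assumed, and a 1.4-point gap is small beside an interval of 3.6% to 11.7%. All of this stands and limits the weight of the point. It does not remove the point, because a separate report does not put the events back into the rates being compared.

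Four stronger readings are tempting, and the documents do not support them.

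- A reader might infer that the rates will be biased low. The rule acts on a deviation's potential to influence outcome, not on the observed outcome, and no document gives the risk in the dropped knees.
- A reader might infer from the Surgical Details form that knees with a non-intact ACL are implanted and then dropped. The form calls for deviation and termination forms but does not say the device was implanted, and section 10.3 lists non-implantation as a termination reason.
- A reader might apply contralateral-UKA counts to all 175 knees. Exclusion 3 bars a history of contralateral-compartment reconstruction, and retrospective knees are screened for visits from 5 years onward, so earlier cases among them are probably screened out.
- A reader might infer that the survivorship endpoint is undefined, or that sections 9.4.3 and 9.4.5 contradict each other. The endpoint wording, and the Adverse Event form's separate fields for revision or removal of study components and for re-operations, point to a non-event when all study components are kept. The two sections read as a general rule with an express exception.

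Excluding a knee with a second implant from the per protocol KSS analysis is also defensible, since its score no longer reflects the study device alone.

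**Conclusion.** The point holds for the safety population and should be fixed. As written, sections 9.4.4 and 9.4.5 take implanted knees out of the adverse event rates that sections 2.2 and 12.3 compare with literature, which does not fit the commitment in sections 9.2.1 and 9.2.2 to summarise all reported events. This rests on reading section 9.2.2 as using the 9.4.4 population.

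The documents determine neither the size nor the direction of any bias. With 9 or 18 of 175 knees dropped and a 7% base rate, the understatement runs from zero at equal risk to 1.4 points at three times the risk. It is larger at a higher base rate or relative risk, and it reverses if the dropped knees do better. The survivorship status of an added contralateral UKA is a minor clarification.

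**What to change.** - **9.4.4:** define the safety population as all subjects implanted with the study device.
- **9.4.5:** remove the safety population from the censoring rule, so that it governs efficacy only. Keep contralateral-UKA knees in the adverse event tables and count one done after the index surgery as a reoperation or adverse event. Their per protocol exclusion from KSS may stay.
- **9.2.2:** name the safety population as the analysis set, flag deviation cases, and add the deviation-free set as a sensitivity table.
- **Minor, 9.1.5 and 9.4.5:** state that an added contralateral UKA with all study components kept is not a survivorship event, and add one sensitivity analysis that counts it as an event.

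The cost is plan wording and a few extra tables. Deviations and re-operations are already recorded, so no new data are needed. The adverse event figures may look slightly less favourable.

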10.1 Subject Recruitment and Screening

Patients will be recruited at the study sites by a review of medical records for prior cases receiving the Triathlon PKR unicompartmental device. Once a patient is identified as having a PKR unicompartmental device implanted outside of the initial prospective study, it will be determined if they are deceased or had the device revised, which would exclude them during the screening process. Once a patient is identified as a potential study candidate, the study coordinator will review all the inclusion and exclusion criteria to ensure the patient meets those criteria. If that screening is successful, the study coordinator will contact the patient to conduct a telephone screening to review the study details and inquire as to the level of interest to participate. If there is interest, it will be determined if the patient has the capacity to give informed consent, and if so, a verbal informed consent will be provided. A signature will be obtained on the formal approved informed consent document to complete the enrollment into study.

10.2 Patient Informed Consent and Guidelines

All subjects for this study will be provided a consent form describing the study and providing sufficient information for subjects to make an informed decision about their participation in this study. The informed consent must contain all elements required by the FDA under 21 CFR part 50; in addition to any other elements required by state, local and institutional policies. See Appendix D for a sample Subject Informed Consent Form. This consent form will be submitted with the protocol for review and approval by the IRB for the study. All subjects must provide

written consent after having had adequate time to consider their participation in the study. The formal consent of a subject, using the IRB-approved consent form, must be obtained before that subject is submitted to any protocol related procedures that are not part of the subject's normal care. Written documentation of consent must be provided on the consent's signature page in addition to a note in the patient medical records indicating the date that consent was obtained. The investigator-designated research professional obtaining the consent must also sign this consent form. The subject or their legal representative should receive a signed copy of the consent according to Good Clinical Practice (GCP) guidelines.

The procedure for obtaining informed consent is outlined below:

- Use a current IRB approved copy of the consent form.
- Review the consent thoroughly with the patient before having him/her sign.
- After the patient has consented to the procedures, ensure he/she sign and date the consent form.
- The person obtaining consent also signs and dates the signature page.
- Provide a copy of the consent to the patient.
- If required, provide the hospital with a copy of the signed consent.
- Maintain the signed original in the patient's study chart.

10.3 Early Withdrawal of Subjects

When and How to Withdraw Subjects

Termination Reason

In the event that the subject is discontinued by the investigative site after discussion with the sponsor prior to the final study evaluation, the subject is notified that they are no longer in the study and a Study Termination CRF will be completed. The following is a list of reasons for which subjects may be terminated, and the date of termination that should be used on the Study Termination CRF in each situation. This list is not all inclusive:

Date of Termination

Tommation Roadon	Date of Fornination
Death	Date of death
Investigative site termination	Date of study close-out visit
Lost to follow-up	Date Stryker termination approval given
Voluntary withdrawal	Date subject notified site of withdrawal

Termination Reason

Revision/removal of study device
Study device not implanted
Surgery not performed

Date of Termination

Date of revision/removal procedure

Date of surgery

Date Stryker termination approval given

If the subject fails to return for their follow-up appointments, every effort should be made to contact the subject to assess his/her health status. If after attempting to contact the subject through three documented phone calls and a certified letter, the subject still does not respond, he/she will be considered lost to follow-up. A Study Termination CRF will be completed only after notifying Stryker of the subject's status and being given approval to terminate.

Study Completion

When a subject completes the study according to protocol, including the final study evaluation, a Study Termination CRF will be completed and the termination date will be the date of the subject's last evaluation.

11 Data Management

11.1 Database

Data will be collected at each site and sent to the Sponsor for entry into a database which will reside at the sponsor site. It is possible that at least one site may record data via an electronic data entry capture (EDC) system. Patient data will be collected, processed, and monitored according to the protocol schedule by the sponsor or sponsor representatives. Sample case report forms are provided in **Appendix E.**

11.2 Confidentiality

This study will comply with the 2002 privacy rule of the Health Insurance Portability and Accountability Act (HIPAA). As such, the Sponsor will obtain an authorization to receive personal healthcare information as part of the informed consent process. In addition, the sponsor will only collect that information which is necessary to support the objectives of the clinical trial and will take precautions to ensure that data received is as de-identified as possible. In the case that some identified information is received, the Sponsor will ensure that any identifying information will not be reported. Study subjects will authorize the Sponsor to use their health information in

support of the clinical trial during the Informed Consent Process. Should a subject choose to withdraw authorization, the Sponsor may use data collected prior to the withdrawal of authorization in order to maintain data integrity.

11.3 Source Documents

Source data is all information, original records of clinical findings, observations, or other activities in a clinical trial necessary for the reconstruction and evaluation of the trial. Source data are contained in source documents. Examples of these original documents, and data records include: hospital records, clinical and office charts, laboratory notes, memoranda, subjects' diaries or evaluation checklists, pharmacy dispensing records, recorded data from automated instruments, copies or transcriptions certified after verification as being accurate and complete, microfiches, photographic negatives, microfilm or magnetic media, x-rays, subject files, and records kept at the pharmacy, at the laboratories, and at medico-technical departments involved in the clinical trial.

All data points collected during follow-up visits must be documented in the patient chart. This includes range of motion values, pain and function as well as complications and additional comments. The Informed Consent process should also be documented in the patient chart. Monitors will be comparing the case report forms against the source documents for accuracy. The monitor will seek to draw a reference between each data point on the CRF and the patient chart. Thus, one cannot derive pain, range of motion or function based on a chart note that reads "Patient doing well." Every effort should be made to ensure complete source documentation.

11.4 Case Report Forms

The study case report form (CRF) is the primary data collection instrument for the study. All data requested on the CRF must be recorded. All missing data must be explained. If a space on the CRF is left blank because the procedure was not done or the question was not asked, write "N/D". If the item is not applicable to the individual case, write "N/A". All entries should be printed legibly in black ink. If any entry error has been made, to correct such an error, draw a single straight line through the incorrect entry and enter the correct data above it. All such changes must be initialed and dated. DO NOT ERASE OR WHITE OUT ERRORS. For clarification of illegible or uncertain entries, print the clarification above the item, then initial and date it.

For specific instructions on CRF completion, please consult the Guide to Case Report Forms. Case report forms should be completed, signed by the investigator, and returned to the sponsor CONFIDENTIAL

within two weeks of the patient evaluation date. If errors or omissions are noted by the sponsor upon receipt of the forms, a data clarification form (DCF) will be sent to the site for clarification. Completed DCFs should be returned to the sponsor within two weeks of receipt.

11.5 Protocol Deviations

Any deviation from this protocol categorized as a 'Major Protocol Deviation' will be recorded by the Sponsor and must be reported to the investigational center's overseeing IRB according to their reporting procedures. Major protocol deviations for this study may include the following; this list may not be all-inclusive:

- Informed consent deviations, including but not limited to:
 - Study procedures performed prior to informed consent
 - Incorrect informed consent version used
- Patient enrolled does not meet the inclusion/exclusion criteria
- Protocol specified study component(s) not implanted
- Off label component usage

If the center anticipates a possible protocol deviation, the investigator or SC should contact Stryker for guidance.

